5.0 Consent Process and Documentation

5.1 Consent Process:

Check all applicable boxes below:

- Informed consent will be sought and documented with a written consent form *[Complete Sections 5.2 and 5.6]*
- Implied or verbal consent will be obtained – subjects will not sign a consent form (waiver of written documentation of consent) *[Complete Sections 5.2, 5.3 and 5.6]*
- Informed consent will be sought but some of the elements of informed consent will be omitted or altered (e.g., deception). *[Complete section 5.2, 5.4 and 5.6]*
- Informed consent will not be obtained – request to completely waive the informed consent requirement. *[Complete Section 5.5]*

The following checkbox is for all locations EXCEPT Penn State Health and College of Medicine:

Exempt Research at all Locations Except Penn State Health and the College of Medicine: If you believe that the research activities outlined meet one or more of the criteria outlined in “HRP-312-Worksheet- Exemption Determination.” Please verify by checking this box that if conducting an exempt research study, the consent process will disclose the following (all of which are included in “HRP-590- Consent Guidance for Exempt Research”):

Penn State affiliation; name and contact information for the researcher and advisor (if the researcher is a student); the activities involve research; the procedures to be performed; participation is voluntary; that there are adequate provisions to maintain the privacy interests of subjects and the confidentiality of the data; and subjects may choose not to answer specific questions.

If the research includes the use of student educational records include the following language in this section (otherwise delete): The parent or eligible student will provide a signed and dated written consent that discloses: the records that may be disclosed; the purpose of the disclosure; the party or class of parties to whom the disclosure may be made; if a parent or adult student requests, the school will provide him or her with a copy of the records disclosed; if the parent of a student who is not an adult so requests, the school will provide the student with a copy of the records disclosed.

Note: If this box has been checked, skip the remainder of section 5 and proceed to section 6 of this protocol. If the investigator’s assessment is inaccurate, an IRB Analyst will request revision to the protocol and that an informed consent form be submitted for review and approval. Except for exemptions where Limited IRB Review (see “HRP-312- Worksheet- Exemption Determination”) is required or where otherwise requested by the IRB, informed consent forms for research activities determined to be exempt without Limited IRB Review are generally not required to be submitted for review and approval by the University Park IRB.

5.2 Obtaining Informed Consent

5.2. 1 Timing and Location of Consent

Participants will be verbally consented for the initial screening up to 14 days before or 21 days after their well-woman appointment over the phone and answers will be input into REDCap by a study team member. Participants will receive a summary explanation of research mailed to their home with study materials.

5.2. 2 Coercion or Undue Influence during Consent

After a review of the research study via the Summary Explanation of Research, subjects will decide if they give consent to participate in the study. Subjects will be reminded that they may refuse to answer any question and end their participation at any time. At all stages of the recruitment and consent process, participants will be reminded that participation is voluntary and that they may withdraw without penalty at any time.

5.3 Waiver of Written Documentation of Consent

5.3. 1 Indicate which of the following conditions applies to this research:

The research presents no more than minimal risk of harm to subjects and involves no procedures for which written consent is normally required outside of the research context.

OR

The only record linking the subject and the research would be the consent document and the principal risk would be potential harm resulting from a breach of confidentiality. Each subject will be asked whether the subject wants documentation linking the subject with the research, and the subject's wishes will govern. *(Note: This condition is not applicable for FDA-regulated research. If this category is chosen, include copies of a consent form and /or parental permission form for participants who want written documentation linking them to the research.)*

OR

If the subjects or legally authorized representatives are members of a distinct cultural group or community in which signing forms is not the norm, that the research presents no more than minimal risk of harm to subjects and provided there is an appropriate alternative mechanism for documenting that informed consent was obtained. *(Note: This condition is not applicable for FDA-regulated research.)*

Describe the alternative mechanism for documenting that informed consent was obtained:

Verbal implied consent

5.3. 2 Indicate what materials, if any, will be used to inform potential subjects about the research (e.g., a letter accompanying a questionnaire, verbal script, implied consent form, or summary explanation of the research)

Verbal script, summary explanation of the research, recruitment card, study flyers, study invitation letter.

5.4 Informed consent will be sought but some of the elements of informed consent will be omitted or altered (e.g., deception).

5.4. 1 Indicate the elements of informed consent to be omitted or altered

Not applicable.

5.4. 2 Indicate why the research could not practicably be carried out without the omission or alteration of consent elements

Not applicable.

5.4. 3 Describe why the research involves no more than minimal risk to subjects.

Not applicable.

5.4. 4 Describe why the alteration/omission will not adversely affect the rights and welfare of subjects.

Not applicable.

5.4. 5 If the research involves using identifiable private information or identifiable biospecimens, describe why the research could not be practicably be carried out without using such information or biospecimens in an identifiable format.

Not applicable.

5.4. 6 Debriefing

Not applicable.

5.5 Informed consent will not be obtained – request to completely waive the informed consent requirement

5.5. 1 Indicate why the research could not practicably be carried out without the waiver of consent

Not applicable.

5.5. 2 Describe why the research involves no more than minimal risk to subjects.

Not applicable.

5.5. 3 Describe why the alteration/omission will not adversely affect the rights and welfare of subjects.

Not applicable.

5.5. 4 If the research involves using identifiable private information or identifiable biospecimens, describe why the research could not be practicably be carried out without using such information or biospecimens in an identifiable format.

Not applicable.

5.5. 5 Additional pertinent information after participation

Not applicable.

5.6 Consent – Other Considerations

5.6. 1 Non-English-Speaking Subjects

We do not plan on soliciting non-English speaking or limited English speaking participants at this time. If unexpectedly encountered, a short form and oral translation process will be used to obtain informed consent. Our institution has translators available to assist.

5.6. 2 Cognitively Impaired Adults

5.6.2.1 Capability of Providing Consent

Not applicable.

5.6.2.2 Adults Unable to Consent

Not applicable.

5.6.2.3 Assent of Adults Unable to Consent

Not applicable.

5.6. 3 Subjects who are not yet adults (infants, children, teenagers)

5.6.3.1 Parental Permission

Not applicable.

5.6.3.2 Assent of subjects who are not yet adults

Not applicable.

6.0 HIPAA Research Authorization and/or Waiver or Alteration of Authorization

6.1 Authorization and/or Waiver or Alteration of Authorization for the Uses and Disclosures of PHI

Check all that apply:

- Not applicable, no identifiable protected health information (PHI) is accessed, used or disclosed in this study. *[Mark all parts of sections 6.2 and 6.3 as not applicable]*
- Authorization will be obtained and documented as part of the consent process. *[If this is the only box checked, mark sections 6.2 and 6.3 as not applicable]*
- Partial waiver is requested for recruitment purposes only (Check this box if patients' medical records will be accessed to determine eligibility before consent/authorization has been obtained). *[Complete all parts of sections 6.2 and 6.3]*
- Full waiver is requested for entire research study (e.g., medical record review studies). *[Complete all parts of sections 6.2 and 6.3]*

- Alteration is requested to waive requirement for written documentation of authorization (verbal authorization will be obtained).** *[Complete all parts of sections 6.2 and 6.3]*

6.2 Waiver or Alteration of Authorization for the Uses and Disclosures of PHI

6.2. 1 Access, use or disclosure of PHI representing no more than a minimal risk to the privacy of the individual

6.2 .1.1 Plan to protect PHI from improper use or disclosure

Information is included in the "Confidentiality, Privacy and Data Management" section of this protocol.

6.2 .1.2 Plan to destroy identifiers or a justification for retaining identifiers

Identifiers will be destroyed after the completion of data collection.

6.2. 2 Explanation for why the research could not practicably be conducted without access to and use of PHI

The proposed study requires enrollment of participants who are getting a clinical Pap/HPV test to compare those results with the findings from a self-sampled HPV test. Identification of these patients would be infeasible using other methods.

6.2. 3 Explanation for why the research could not practicably be conducted without the waiver or alteration of authorization

The waiver is necessary in order to screen participants for eligibility using the patient's medical record prior to their consent to participate in this study. This method will allow study team members to efficiently identify patients who are receiving/have received a Pap/HPV test. Many well-woman exams do not require a Pap/HPV test and it is not practical to provide information to all of these patients.

6.3 Waiver or alteration of authorization statements of agreement

Protected health information obtained as part of this research will not be reused or disclosed to any other person or entity, except as required by law, for authorized oversight of the research study, or for other permitted uses and disclosures according to federal regulations.

The research team will collect only information essential to the study and in accord with the 'Minimum Necessary' standard (information reasonably necessary to accomplish the objectives of the research) per federal regulations.

Access to the information will be limited, to the greatest extent possible, within the research team. All disclosures or releases of identifiable information granted under this waiver will be accounted for and documented.

7.0 Study Design and Procedures

7.1 Study Design

After identification, a study team member will talk with potential participants over the phone to determine those that meet the study eligibility criteria. HPV self-sampling kits, with the summary explanation of research, will be mailed to study participants to complete within a week.

If a participant is contacted prior to their well-woman appointment: 3-5 days before the well-woman appointment, the research project manager will reach out to check if study participants have completed their HPV self-sampling kit. Those that have completed the kit will complete a survey over the phone and get an appointment reminder. They will mail their HPV self-sampling kit to the Penn State Health clinical lab. Those that have not completed their HPV self-sampling kit will get instructions to not use the HPV self-sampling kit before the well-woman and get an appointment reminder. They will be told they can complete the HPV self-sampling kit one week after their appointment. If the first self-sampling kit is lost or not received, we will mail a second self-sampling kit. They will then go to their appointment where the clinician will perform the Pap smear/HPV test. If the participant did not complete the self-sampling kit, two weeks after the well-woman appointment a study team member will schedule a time to call the participant to determine if she completed the HPV self-sampling kit and, if so, complete a survey over the phone. If the participant is not able to be reached or has not completed the HPV self-sampling kit, the study team will perform up to three follow up calls per participant. Once an HPV self-sampling kit has been completed and the analysis has been received from the Penn State Health Clinical lab, study participants will be mailed their compensation within 1 week. Only one sample per participant will be mailed to the Penn State Health Clinical lab where they will receive and analyze each sample. Analysis of the self-sampling specimens will be conducted to determine HPV DNA positivity to compare to results of the previous Pap/HPV test. In the unlikely event that not enough sample is collected, the participant will still be compensated for their efforts, and the study team will take note of how much sample was deemed too little for analysis and they will be excluded from data analysis. EMR data will be used to check insurance status, and the date and result of PAP/HPV tests

If a contacts the study team after their well-woman appointment: The patient will reach out to the research project manager to check eligibility. If eligible, the research project manager will send a kit and summary explanation of research and ask the patient to complete the kit within two weeks. Remaining procedures will be identical to the procedures for participants contacted prior to their well-woman appointment.

If a patient is contacted after their well-woman appointment: The study team will reach out to the patient to check eligibility. If eligible, the research project manager will send a kit and summary explanation of research and ask the participant to complete the kit within two weeks. Remaining procedures will be identical to the procedures for participants contacted prior to their well-woman appointment.

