7.2 Study Procedures

Survey and HPV self-sampling kit

7.2. 1 10-14 days before/after the well-woman appointment

A study team member will obtain verbal consent from the participants to screen them for eligibility, and if they are eligible and agree to participate, a study team member will mail a self-sampling kit and summary explanation of research to be completed within 1 week.

7.2. 2 3-5 days before the Well-Woman appointment OR 13-21 days after Well-Woman appointment

Study physicians will perform the Pap smear/HPV test per standard clinical guidelines. Participants will complete the HPV self-sampling kit on their own time and mail it to the Penn State Health Clinical lab in a pre-labeled package provided by the study team.

3-5 days before the Well-Woman appointment: A study team member will call study participants to provide a reminder to attend their well-woman appointment (if necessary) and take a survey over the phone if they completed their HPV self-sampling kit. Those that did not complete the HPV self-sampling kit will get an appointment reminder (if needed) and be told not to use the self-sampling kit until after the Well-Woman appointment. They will be told they can complete the HPV self-sampling kit a week after their appointment.

13-21 days after Well-Woman appointment: For participants who did not complete their HPV self-sampling kit before their well-woman appointment, a study team member will call study participants to ascertain if they completed their HPV self-sampling kit and take a survey over the phone. If they still have not completed it or could not be reached, the study team will contact them up to 3 more times to gather information. Although participants must collect their sample within 21 days of their well-woman appointment, participants may be called up to seven days past day 14 in order to account for weekends and holidays and to give participants time to return phone calls if necessary. Participants will not be contacted after day 21.

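### Under Section 7.1 only kit users are surveyed, and Section 8.3 plans no inadequate-sample or kit-completion result; Sections 7.1 and 7.2.2 differ on who is asked

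*Combined protocol and SAP*

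**What the plan says.** **Inadequate samples.** Section 7.1 provides that "the study team will take note of how much sample was deemed too little for analysis and they will be excluded from data analysis". The exclusion is not limited to the comparison of test results. No repeat is provided for: "Only one sample per participant will be mailed to the Penn State Health Clinical lab", and a second kit is sent only in a different case: "If the first self-sampling kit is lost or not received, we will mail a second self-sampling kit".

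**Survey.** Section 7.1 makes the survey conditional on kit use at both calls. Before the visit: "Those that have completed the kit will complete a survey over the phone and get an appointment reminder". After the visit, the call is to "determine if she completed the HPV self-sampling kit and, if so, complete a survey over the phone". Section 7.2.2 repeats the condition before the visit ("take a survey over the phone if they completed their HPV self-sampling kit") but not after it, where the caller is to "ascertain if they completed their HPV self-sampling kit and take a survey over the phone". Its next sentence allows up to three further contacts with women who have not completed the kit or were not reached. The purpose is to collect information, but the content is not described. The limit is firm: "Participants will not be contacted after day 21".

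**Non-completers.** Section 3.3 removes women who do not finish the study activities, documents the withdrawal, and replaces them if time permits. Section 7.4.4 confirms compliance from the laboratory result.

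**Analysis.** Section 8.3 plans Fisher's exact tests, Cohen's kappa and descriptive survey summaries. It names no inadequate-sample, completion or return proportion, and has no rule for unsatisfactory clinician samples.

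**The concern.** Section 1.1 sets out to compare the test characteristics of the two collection methods. Section 1.3 uses acceptability and barriers to judge whether self-sampling could serve as an alternative to clinic screening. A kit that is never used, or that yields too little material, bears on both questions.

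If 7.1 is followed as written, acceptability is measured only among women who managed to use the kit. If the exclusion is read literally, women who used it but returned too little sample also lose their survey answers. Women who did not use it leave the study, and no result is planned that counts them. The viability question would then be answered from women for whom the kit worked, with nothing beside it to show how many others there were.

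**Working it through.** **1. The plan's own figures.** Section 15.2 gives at least 113 potentially eligible patients a month, about 7 months, 790 invited and 25% agreeing.
- 113 × 7 = 791, which matches 790 invited.
- 790 × 0.25 = 197.5, which matches the target of 197.

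The number expected to agree therefore equals the number wanted for analysis, with no explicit inflation for losses. The 197 in Section 8.2 cannot be re-derived, because no agreement rate, prevalence, margin or attrition rate is given.

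**2. Who is surveyed, side by side.**

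| Call | Section 7.1 | Section 7.2.2 |
|---|---|---|
| Before the visit | kit users only | kit users only |
| After the visit | kit users only | condition not stated; further contacts with non-completers, content unspecified |

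Three of the four cells restrict the survey to kit users. The fourth can be read either way, and nothing gathered from non-users is linked to an analysis.

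The documents give no rates for the next three steps. **All rates below are assumptions, and each range includes no effect.**

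**3. Kit completion.** With completion proportion c and replacement until 197 complete, the number sent a kit is 197/c, rounded up. Without replacement, the number of completers is 197 × c.

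| c | Women sent a kit | Non-completers | Completers without replacement |
|---|---|---|---|
| 100% | 197 | 0 | 197 |
| 90% | 219 | 22 | 177 |
| 80% | 247 | 50 | 158 |
| 70% | 282 | 85 | 138 |

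Under 7.1, the non-completers appear in no planned result. Under the looser reading of 7.2.2, some would have given information, but with no analysis specified for it.

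**4. Inadequate samples.** With a fraction f of 197 returned samples inadequate, the count is 197 × f. The intervals are exact (Clopper-Pearson) 95% intervals for the proportion that is not planned.

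| f | Inadequate | Valid pairs | Proportion (95% CI) |
|---|---|---|---|
| 0% | 0 | 197 | 0% (0 to 1.9) |
| 1% | 2 | 195 | 1.0% (0.1 to 3.6) |
| 5% | 10 | 187 | 5.1% (2.5 to 9.1) |
| 10% | 20 | 177 | 10.2% (6.3 to 15.2) |

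The proportion would be estimated with useful precision, including when no sample fails.

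**5. Optional sensitivity analysis.** Suppose positive agreement among valid pairs is 90%, and inadequacy is as common in clinician-positive women as in the rest. Counting inadequate samples as not detected gives 0.90 × (1 − f).
- For f = 0, 1, 5 and 10% this is 90, 89.1, 85.5 and 81%.
- With 20 clinician-positive women, 2 of them inadequate: 16/18 = 88.9% (65.3 to 98.6) against 16/20 = 80.0% (56.3 to 94.3). The intervals overlap widely.
- With 20 clinician-positive and 177 negative women and 90% agreement in each group, kappa is 0.593. At f = 10%, positive agreement becomes 81%, negative agreement 0.90 × 0.90 + 0.10 = 91%, and kappa 0.567.

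This is descriptive only.

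**The case against.** The strongest reply is that the information is already collected. Inadequate samples are noted, withdrawals are documented, and the laboratory result confirms compliance. In 7.1 the exclusion comes directly after the comparison of HPV positivity with the clinic result, so it most naturally means that comparison. Agreement and kappa do need valid pairs, and that restriction is legitimate. All of this stands. What it leaves open is that no denominator is fixed and no result is planned, so reporting is optional. Answers never requested from non-users cannot be recovered later.

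A reader might infer more than the documents support:
- **That failures vanish from the record.** They do not. The gap is in the planned results.
- **That non-users are never asked anything.** Section 7.2.2 has them contacted again; only the content and its use are unspecified.
- **That the survey results will be too favourable.** This is plausible for acceptability but not shown. For barriers it is unsupported: Section 1.3 concerns barriers to cervical screening, not to kit use, and every participant is already attending in-office screening.
- **That recruitment cannot absorb losses.** Section 15.2 says at least 113 a month and approximately 7 months, and Section 3.3 allows replacement. Only an explicit inflation is absent.

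Completion is also an imperfect measure here. Section 5.2.2 has women decide after reviewing a summary that is mailed with the kit, so some non-users may simply have declined. Reminder calls, the instruction to wait until after the visit, and payment all affect completion.

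**Conclusion.** The point holds, at minor to moderate severity. Under 7.1 as written, acceptability comes only from kit users, a selected group for the question in Section 1.3. Women with inadequate samples are excluded by a phrase whose scope is probably the paired comparison but is not limited to it. Section 8.3 plans no inadequate-sample or completion result, and 7.1 and 7.2.2 do not agree on the post-visit survey.

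The size is unknown and may be nil. Section 7.1 calls too little sample unlikely and gives no rate, and the documents give no completion rate either. The tables show what would follow from assumed rates and are not forecasts. The conclusion that results are missing rests on the text and not on those rates. The paired analysis on valid pairs does not need to change.

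**What to change.** 1. **Inadequate samples.** In 7.1, limit the exclusion to the paired agreement and kappa analysis, and keep these women's survey answers. In 8.3, report the inadequate proportion of returned self-samples with an exact 95% interval, and unsatisfactory clinician samples in the same way. Counting inadequate samples as not detected among clinician-positive women is an optional descriptive sensitivity analysis; it would require positive agreement to be named in 8.3.
2. **Completion.** In 3.3 and 8.3, report kit completion and return over all eligible women who verbally agreed and were mailed a kit. Count each woman once, even if a second kit is sent, and include those later replaced. Show separately any who declined after reading the mailed summary. Note that the study's calls, timing instructions and payment affect completion.
3. **Survey.** Align 7.1 with 7.2.2. On the post-visit calls already planned, and within the existing day-21 limit, ask women who have not used the kit the barrier questions, the acceptability questions that can be answered without use, and their reason for non-use. Report results by kit use, give the number not reached, and label any acceptability figure from kit users only as such.

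**Cost.** Slightly longer calls, a possible IRB amendment to the call script, and a few table lines. The team must mark which survey items can be answered without use, since the instrument is not in the documents. Women not reached by day 21 remain missing and can only be counted. The figures may look less favourable. The sample size and visits do not change.
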